6.5.3 Adverse Events

Summary Tables

Goal: To present adverse events organized by drug dose, defined here as total amount of study drug per session near AE or reaction, including initial dose and supplement if administered, , seriousness, severity and relatedness to the study drug

Population: All enrolled, Intention to treat, Per protocol, Partial crossover, Extended Assessment 1, Extended Assessment 2

Categorical data includes: Number of AEs per subject; Number of severe AEs; Instances of occurrence of each spontaneously reported reactions by condition (MDMA, Placebo) and Stage (Stage 1, Stage 2); Adverse events (AE identity, seriousness (Yes/No), severity (mild, moderate, severe), onset, resolution, relatedness to study drug (not related, possibly related, probably related); Spontaneously reported reactions listed by MedDRA (Version 14) System Order Class

Format of presentation: This data will be presented in several summary tables of counts per subject, by drug dose, or across the course of the study, as appropriate for the data or descriptive statistics being listed.

Content of Presentation: Number of AEs per subject; Number of severe AEs; Instances of occurrence of each spontaneously reported reactions by condition (MDMA, Placebo) and Stage (Stage 1, Stage 2), number of severe spontaneously reported reactions;Adverse events (AE identity, seriousness (Yes/No), severity (mild, moderate, severe), onset, resolution, outcome, relatedness to study drug (not related, possibly related, probably related); Spontaneously reported reactions listed by MedDRA Version 14 System Order Class

Descriptive data includes: Overall number of AEs, severity of AEs, Peak Demeanor after each experimental and open label session, Overall number of spontaneously reported reactions, average reported severity of spontaneously reported reactions

Format of Presentation: Summary tables of frequency listings in total, by condition, by session, by subject and by condition

Content of Presentation: Adverse Event Listings (All possibly and probably related AEs, all AES occurring within seven days of drug administration, all severe AEs, and number of severe AEs by condition); AE or severity of AE and peak demeanor after each experimental or open label session by condition (MDMA, placebo, partial crossover).

Tabular Listing of Adverse Events

Goal: To follow guidance for display of adverse events

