Population: All enrolled, intention to treat, per protocol, partial crossover, Extended Assessment 2

Data included: Per each AE; Subject number, Patient identifier

- Age, race, sex, weight (height, if relevant)
- Location of CRFs, if provided
- Adverse event description (preferred term, reported term)
- Duration of the adverse event
- Severity (e.g., mild, moderate, severe)
- Seriousness (serious/non-serious)
- Action taken (none, dose reduced, treatment stopped, specific treatment instituted etc.)
- Outcome (e.g., CIOMS format)
- Relatedness process of determination given if possible
- Date of onset or date of clinic visit at which the event was discovered
- Timing of onset of the adverse event in relation to last dose of investigational product (if or when applicable)
- Investigational product dose in absolute amount, mg/kg
- Duration of investigational product treatment (Stage 1, Stage 2, Stage 3)
- Concomitant treatment during study.

Format of presentation: All adverse events for each patient, including the same event on several occasions will be listed, giving both preferred term and the original term used by the investigator. The listing should be by treatment group and will include:

Analysis #1

Goal: To see if one or more demographic factor and condition alter the number and severity of adverse events and spontaneously reported reactions collected across the course of the study.

Population: All enrolled, intention to treat, per protocol, partial crossover, Extended assessment 1, Extended assessment 2

Data included: Number of AEs collected across Stage 1, Stage 2 and Stage 3, and any AEs collected before 2, 6 and 12 month follow up for Extended Assessment 1 participants, Number of severe AEs collected across Stage 1, Stage 2 and Stage 3 (when applicable), average severity rating of AEs occurring during the study, number of individual spontaneously reported reactions and average severity of self-reported reactions.

Format of analysis: Two-way ANOVA for gender, linear regression analysis for age

Between-groups factors: Condition (125 mg MDMA, 25 mg MDMA, 150 mg MDMA (when applicable)); gender; age

Analysis #2

Goal: to see if there is an effect of presence versus absence of supplemental dose upon number of AEs and spontaneously reported reactions and number of severe AEs and spontaneously reported reactions.

Population: All enrolled, intention to treat, per protocol, partial crossover, extended assessment 2

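### The SAP tests average adverse-event severity against condition, a score that mild events dilute and that cannot register a rise shared by all grades; worst severity per participant should replace it

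*SAP*

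**What the plan says.** The stated goal of SAP 6.5.3 Analysis #1 is "To see if one or more demographic factor and condition alter the number and severity of adverse events and spontaneously reported reactions". Its data list contains "Number of AEs collected across Stage 1, Stage 2 and Stage 3", then "Number of severe AEs collected across Stage 1, Stage 2 and Stage 3 (when applicable", and then "average severity rating of AEs occurring during the study, number of individual spontaneously reported reactions and average severity of self-reported reactions". The test is "Two-way ANOVA for gender, linear regression analysis for age", with condition as a between-groups factor. I read the self-reported reactions in that list as the spontaneously reported reactions named elsewhere in the section.

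The Summary Tables part of 6.5.3 also presents "average reported severity of spontaneously reported reactions", next to "number of severe spontaneously reported reactions" and listings of severe adverse events with counts by condition. SAP 6.5 presents the maximum intensity of spontaneously reported reactions. Adverse events are graded as "severity (mild, moderate, severe"; no levels are given for reactions.

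The SAP gives no numeric score for the grades. It does not say whether the average is taken within participants or over pooled events, or what happens to a participant with no events.

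**The concern.** The denominator of an average severity is the number of events. A treatment that adds many mild reactions to the same or more severe ones can lower its own average. That pattern is plausible here. Protocol 2.8.1 chose the low dose for minimal though detectable effects, and it expects the side-effect profile to increase at the highest dose. A participant who tolerates treatment perfectly has no average at all and, unless a rule is written, would leave the analysis.

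At stake is a planned inferential result on severity by condition that could read as reassuring about the full dose when the full dose was worse.

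**Working it through.** There is no figure in the plan to reproduce. The SAP gives no event rates and no power for this analysis.

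**Inputs.** Allocation is 8 full dose and 4 low dose (Protocol 2.8.1). There are three severity grades (SAP 6.5.3). Scores of 1, 2 and 3, averaging within participant, omission of participants without events, and all event rates are my assumptions.

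**Dilution.** Average = (mild + 2 × moderate + 3 × severe) / number of events. If the average over n events is m, one more mild event changes it by (1 − m)/(n + 1). This is negative whenever m exceeds 1 and zero when every event is mild. One moderate plus one severe event gives 5/2 = 2.50. Adding 2, 4, 6, 8 or 10 mild events gives 1.75, 1.50, 1.375, 1.30 and 1.25.

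**Reversal between two participants.** One mild plus one moderate: 3/2 = 1.50. Six mild, one moderate and one severe: (6 + 2 + 3)/8 = 1.375. The second participant scores as milder, yet has the higher worst grade (severe against moderate), more severe events (1 against 0) and more events (8 against 2).

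**No response to a proportional rise.** Means of 2/1/0.25 (mild/moderate/severe per participant) give (2 + 2 + 0.75)/3.25 = 1.46. Doubling every grade gives (4 + 4 + 1.5)/6.5 = 1.46.

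**Simulation.** 20,000 trials per scenario, 8 against 4, with Poisson counts per participant and grade. In every scenario the full dose is worse at every grade. The expected average applies the formula to the mean counts. The last column is the share of trials in which the full-dose arm had the lower mean of participants' averages.

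| Low dose | Full dose | Expected average, low / full | Full dose looks milder |
|---|---|---|---|
| 3/1/0.1 | 4.5/3/0.3 | 1.29 / 1.46 | about 15% |
| 3/1/0.1 | every grade ×2 or ×3 | 1.29 / 1.29 | about 47% |
| 2/1/0.25 | 4/2/0.5 | 1.46 / 1.46 | 48% |
| 1/1/0.25 | 3/2/0.5 | 1.67 / 1.55 | 65% |
| 3/1/0.1 | 9/1.5/0.3 | 1.29 / 1.19 | about 72% |
| 2/1/0.1 | 8/2/0.2 | 1.39 / 1.24 | 78% |
| 1/1/0.25 | 6/2/0.5 | 1.67 / 1.35 | 88% |
| 1/1/0.125 | 6/1.5/0.25 | 1.59 / 1.26 | 91% |

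In the 9/1.5/0.3 scenario, mean worst severity (none = 0) was about 2.1 on full dose against 1.75 on low dose. It pointed the wrong way in about 15% of trials, compared with 72% for the average.

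**Undefined values.** The chance of no event is exp(−total mean). With low-dose means of 3/1/0.1 it is exp(−4.1), under 2%. With sparse low-dose means of 0.7/0.25/0.02 it is exp(−0.97) = 38%. With full-dose means of 2.1/0.375/0.06 it is exp(−2.535) = 8%. That sparse pair gives a reversal in about 54% of trials. In the five scenarios that start from low-dose means of 1/1 or 2/1 mild/moderate, 16% to 40% of trials had at least one participant with no average.

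**Companion counts.** In the trials where the average reversed, the total number of adverse events was higher per participant on full dose in 97% to 100%. The severe count is a weaker guard. In those same five scenarios it was higher on full dose in 59% to 72% of all trials. In the sparse case, exp(−(4 × 0.02 + 8 × 0.06)) = exp(−0.56) = 57% of trials have no severe event in either arm.

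**The case against.** A reader might infer that the average is the only severity measure tested, so that the safety analysis would hide a worse full-dose profile. The documents do not support that. The number of adverse events and the number of severe ones stand in the same data list, and Analyses #2 and #3 use them again by dose. Severe events are listed by condition, maximum intensity of reactions is presented, and every adverse event is listed with its grade. With 12 participants, a reader could work out worst grades by hand.

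A reader might also infer that the average could give the wrong answer to the trial's first question. That question concerns serious adverse events, and seriousness is recorded separately from severity.

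Nor do the documents show that participants without events would be dropped, or that these would be mainly low-dose participants. The SAP is silent, and the share depends on rates it does not give.

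Finally, the simulated percentages compare arm means, not significance. In the 9/1.5/0.3 scenario, a t-test finds the full dose significantly milder in only about 13% of trials. Where moderate and severe events rise faster than mild ones, the average usually points the right way.

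All of this stands, and it limits the consequence. It does not make the average a valid severity measure. It also does not cover spontaneously reported reactions: Analysis #1 gives them a count and an average only, and although the goal of Analysis #2 mentions severe reactions, its data list holds adverse events alone.

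**Conclusion.** The concern holds in a limited form. Average severity, as tested in Analysis #1, does not measure severity burden. It is diluted by mild events once any event exceeds mild, it is blind to a proportional rise across grades, and it is undefined without events. When the full dose is worse at every grade, it looked milder in about 15% to 91% of simulated trials. The range reflects which grades rise most, and it rests on assumed Poisson rates, 1/2/3 scoring and within-participant averaging.

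Only the average-severity result would mislead. For adverse events, the tested counts, chiefly the total, would still show the excess. For spontaneously reported reactions, no tested data list holds another severity measure, so there the protection is descriptive only. The change should be made, but the safety report does not fail without it.

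**What to change.** In SAP 6.5.3 Analysis #1, replace both averages with the worst severity per participant, coded none = 0, mild, moderate, severe, and analyse it as an ordered score, for example by ranks. Participants with no events then stay in. Take the worst grade within the dose being compared, because a low-dose participant who enters Stage 2 also receives the full dose. State the grades used for spontaneously reported reactions.

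Tabulate, by dose received and session, the number and percent of participants with at least one moderate or severe event, for adverse events and for reactions. Keep the existing counts, since worst severity does not show repetition. In the Summary Tables, drop the average severity of reactions, or label it descriptive and print it beside counts by grade.

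The SAP already plans to report adverse-event severity and maximum intensity of reactions, so no new data are needed. The cost is a small wording change and slightly more tabulation.

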With participants carefully monitored for any indicators of adverse events, the initial doses of either 125 mg or 150 mg, and the cumulative dose of 187.5 mg or 225 mg respectively will prove to be tolerable and pose no more than minimal risk. The side effect profile is expected to increase with the higher dose but it is considered unlikely that there will be any Serious Adverse Events (SAEs) or any persisting side effects.

Table 1. Dose Regimen

	Initial Dose	Supplemental Dose	Cumulative Dose
Low Dose	25 mg	12.5 mg	37.5 mg
Fully Active Dose	125 mg	62.5 mg	187.5 mg
20% Larger Active Dose	150 mg	75 mg	225 mg

Supplemental doses for both the Low and the Fully Active dose conditions were chosen to be half the size of initial doses, and the dosage and schedule of dosing was chosen on the basis of case reports describing the use of MDMA in psychotherapy (Greer and Tolbert 1998; Stolaroff 2004, Styk 2007). Supplemental dosing performed 2.5 hours after the initial dose is expected to extend the course of drug effects without increasing their intensity. Both the Low and Fully Active dose conditions use supplemental doses that are half of the initial dose, to make dosing schedule equivalent across the conditions.

Participants will receive an initial dose of MDMA approximately 1 to 1.5 hours after they arrive at [name] office for each experimental session. If the investigators believe the participant is able to tolerate a supplemental dose and the participant agrees to take it, then a supplemental dose will be offered 2.5 hours later. The investigators will not administer the supplemental dose if the participant is exhibiting signs or symptoms that would place him or her at greater risk of experiencing a serious adverse event.

Each dose will consist of the specified amount of racemic MDMA mixed with an inactive substance, such as lactose, to prevent the investigators from distinguishing doses through weight or appearance of the capsules. Initial doses will be distinguished from supplemental doses through labeling them "Dose 1" and "Dose 2" or "first" and "second" dose to ensure that the correct dose is administered at the scheduled time. Each dose of MDMA will be administered along with 250 to 300 mL electrolyte-containing fluid. MDMA will be administered during each of the three experimental sessions, with the second and third session scheduled to fall two to four weeks after the previous experimental session.

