The subject will be required to give written informed consent to take part in Stage 3 of the study, with consent given separately from the initial consent. If the participant consents to take part in Stage 3 of the study, he or she would receive an initial dose of MDMA that will either be identical to that used in Stage 1 and 2 or that of 150 mg, followed by a supplemental dose of up to 75 mg 2.5 hours later, during two experimental sessions scheduled two to four weeks apart. The investigators will use clinical judgment as the basis for determining initial and supplemental dose for each of the two Stage 3 sessions, and they may use their judgment to employ a different dose during the second session on the basis of their experience during the first Stage 3 session. Outcome measures administered 2 months (T3) after the third experimental session will serve as baseline measures for Stage 3. The participant would undergo one preparatory non-drug psychotherapy session 1 to 2 weeks prior to the first experimental session, and he or she would receive non-drug psychotherapy follow-up sessions according to the same schedule described for stage 1 of the controlled study. Procedures for non-drug psychotherapy sessions, experimental sessions, weekly telephone contact and outcome measure administration will be the same as those employed in the first stage of the study.

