Data included: Number of AEs across all study stages, number of severe AEs across all study stages

Format of analysis: One-way ANOVA

Between groups factor: Dosage (25 mg MDMA, 37.5 mg MDMA, 125 mg, 187.5 mg, 150 mg MDMA, 212.5 mg MDMA, 225 mg MDMA)

Analysis #3

Goal: To see if demographic variables interact with dose of study drug; performed if and only if a previous analysis establishes that gender, age or presence of another affective disorder produce an interaction with condition.

Population: All enrolled, intention to treat, per protocol, partial crossover, Extended assessment 1, Extended assessment 2

Data included: Number of AEs across all study stages, number of severe AEs across all study stages.

Format of analysis: Two-way ANOVA for categorical data, regression analysis for continuous data

Between-group factors: Demographic factor (gender (male, female), age, presence of another affective disorder), study drug dose (25 mg, 37.5 mg, 125 mg, 187.5 mg, 150 mg, 212.5 mg, 225 mg MDMA)

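### The adverse-event analysis of the supplemental dose uses a seven-level total-dose ANOVA, which can reject because initial doses differ even if the supplement has no effect

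*SAP*

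**What the plan says.** The goal of Analysis #2 in SAP 6.5.3 is "to see if there is an effect of presence versus absence of supplemental dose upon number of AEs", and likewise on severe AEs and spontaneously reported reactions. The method is "Format of analysis: One-way ANOVA", with one factor: "Between groups factor: Dosage (25 mg MDMA, 37.5 mg MDMA, 125 mg, 187.5 mg, 150 mg MDMA, 212.5 mg MDMA, 225 mg MDMA". The outcome is "Data included: Number of AEs across all study stages, number of severe AEs across all study stages". No contrast, pairwise comparison or separate supplement term is named. Analysis #3 in the same section reuses the seven dose levels.

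Earlier in 6.5.3, drug dose is "defined here as total amount of study drug per session near AE or reaction, including initial dose and supplement if administered". Each level is therefore an initial dose with or without its supplement.

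For vital signs and Subjective Units of Distress, SAP 6.5.1 Analysis #2 handles the same kind of question differently: condition and supplement (given or not given) are two separate factors.

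The supplement is not assigned at random. Protocol 2.8.1 makes it conditional: "If the investigators believe the participant is able to tolerate a supplemental dose and the participant agrees to take it". Protocol 2.8.5.1 repeats that it is offered only when the therapists see no warning signs.

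**The concern.** The question has one degree of freedom: supplement taken or not, at a given initial dose. The test asks whether any of seven total doses differs from any other. The seven levels mix three initial doses with the supplement, so the test cannot say which of the two caused a rejection.

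The documents make an initial-dose difference plausible. Protocol 2.8.1 chose the low dose because its subjective effects are barely noticeable. Protocol 4.2 expects little physiological effect at 25 mg but marked rises in blood pressure and heart rate at 125 mg. These are not AE counts, but they make equal AE means at 25 and 125 mg an unlikely starting point.

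Tolerability of the supplement is part of the first hypothesis in Protocol 2.6, and Protocol 4.2 says that the physiological effects of such a second dose are not yet known. In the AE section, this is the one inferential test whose stated goal is the supplement. A significant result could be read as a supplement effect when it is not one, and a non-significant result is weak evidence that the supplement is harmless.

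**Working it through.** The documents give no power or error rate for this analysis, so there is no stated figure to reproduce.

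**1. What the seven levels contain.** Protocol 2.8.1: "Supplemental doses for both the Low and the Fully Active dose conditions were chosen to be half the size of initial doses". Protocol 2.8.7, for Stage 3: "followed by a supplemental dose of up to 75 mg 2.5 hours later". Hence:

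- 25 mg initial dose: 25 and 25 + 12.5 = 37.5
- 125 mg initial dose: 125 and 125 + 62.5 = 187.5
- 150 mg initial dose: 150, 150 + 62.5 = 212.5 (inferred) and 150 + 75 = 225

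The 7 − 1 = 6 df split into 2 for initial dose and 1 + 1 + 2 = 4 for supplement within initial dose.

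**2. Rejection when the supplement effect is exactly zero.** Alpha is 0.05 (Protocol 2.8.3). Let 125 and 150 mg both lie d standard deviations above 25 mg. The noncentrality is λ = Σ nᵢ(μᵢ − μ̄)²/σ², which reduces to d² × n(low) × n(high)/N. Supplement uptake drops out.

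Two units of analysis, assuming that all four low-dose participants enter Stage 2 and that observations are independent:

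- Sessions: 8 × 3 = 24 full-dose and 4 × 3 = 12 low-dose in Stage 1, 4 × 3 = 12 in Stage 2, 3 × 2 = 6 in Stage 3; total 54. λ = d² × 12 × 42/54 = 9.33 d², F on 6 and 47 df.
- Subject-stages: 4 low + 8 full + 4 Stage 2 + 3 Stage 3 = 19. λ = d² × 4 × 15/19 = 3.16 d², F on 6 and 12 df.

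| d | 54 sessions | 19 subject-stages |
|---|---|---|
| 0 | 5.0% | 5.0% |
| 0.5 | 14.9% | 7.1% |
| 1 | 54.3% | 14.7% |
| 1.5 | 91.8% | 30.2% |
| 2 | 99.7% | 52.3% |

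**3. The same with counts.** Simulated Poisson AEs in 54 sessions, an assumed 7 of them without supplement, and no supplement effect. Rejection by the seven-level F-test for rate ratios 1.5 / 2 / 3 (125–150 mg against 25 mg):

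- 0.3 AEs per low-dose session: about 7 / 10 / 21%
- 1 AE: about 10 / 28 / 82%
- 2 AEs: about 18 / 61–63 / 99%

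A 1-df supplement term adjusted for initial dose rejects about 4–5% in these scenarios.

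**4. Dilution of a real effect.** With no initial-dose effect, 1 AE per session without supplement and 1 more with it, power in the layout of step 3 is about 10–11% for the F-test and 41–43% for the 1-df term. With normal data, a 1 SD supplement effect and 80% uptake, it is 48% against 80%.

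**5. Stress test of the two-term model.** The 4–5% in step 3 assumes that withholding is unrelated to AEs. Now keep the supplement effect at zero but let sessions without supplement have twice the AE rate (base 1 AE). The 1-df term falsely rejects about 60% of the time at rate ratio 1 and about 78% at rate ratio 2. The seven-level F-test rejects about 40% and just under 80%.

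**The case against.** Several points on the other side stand.

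- A reader might infer that the planned test will reject whenever the supplement is inert. It need not. Without an initial-dose effect it holds its level near 5%, and with one record per subject-stage the excess is modest. The SAP does not fix the unit: it counts AEs over all stages, lists AEs per subject elsewhere, yet defines dose per session.
- A reader might cite the Protocol 2.8.1 remark that side effects should increase with the higher dose as proof that 25 and 125 mg differ. In context it compares 150 with 125 mg, initial and cumulative dose together, so it does not show that.
- A reader might infer that a significant result would be reported as a supplement effect. The SAP gives no interpretation rule, and its AE tables by total session dose would put 25 beside 37.5 mg and 125 beside 187.5 mg.
- A reader might infer that separating the two terms gives a calibrated test. Step 5 shows otherwise: if the supplement is withheld or declined because AEs have already begun, the two-term test can mislead as badly as the planned one.
- Tolerability of the supplement will also be judged from AE listings, vital signs and distress scores. No efficacy conclusion depends on this test.

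These points limit the size of the problem and what a corrected analysis can claim. None makes the seven-level F-test answer the stated question.

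**Conclusion.** The stated goal and the named test do not match, and the SAP has no contrast that repairs this. The omnibus test can attribute an initial-dose difference to the supplement, and it has low power for the supplement itself.

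The figures are scenarios. The range of about 10% to 82% belongs to 54 independent sessions at 1 AE per low-dose session. A lower AE rate or a subject-stage unit gives much smaller values, and a higher rate gives larger ones. Within-participant correlation was left out of every calculation.

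The change should be made, as an alignment of a secondary safety analysis. It has no bearing on the primary CAPS comparison.

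**What to change.** In SAP 6.5.3 Analysis #2, replace the seven-level factor as follows:

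- Analyse AE counts per session, so that each count maps to one dose.
- Enter initial dose (25, 125, 150 mg) and supplement (given, not given) as separate terms, following SAP 6.5.1 Analysis #2.
- Add a participant effect, because participants contribute several sessions and may cross stages.
- Report the supplement estimate within initial dose with a 95% CI, and the number of sessions in each cell. Some cells without supplement may be very small or empty.
- State that supplement-taking was not randomized, being withheld on tolerability or declined, so the estimate is observational and may be confounded by AEs that began before the supplement was due.

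Use the same two terms in Analysis #3.

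The cost is wording plus slightly more analysis work. No new data should be needed: the AE listing in 6.5.3 already calls for onset date, timing relative to the last dose, and dose.
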